10 DOSING DELAYS/MODIFICATIONS

All subjects enrolled in the phase 1 portion will start treatment on the assigned dose per cohort based on the dose escalation algorithm provided. No dose delays or modifications are allowed during this period. All subjects enrolled in the phase 2 portion may have the following dose delays/modifications once the MTD has been defined.

Ruxolitinib may be held by the Investigator at any time if there is concern about subject safety. Dosing must be halted immediately if either of the following occurs:

- Platelet counts fall below 10,000/μL and/or a life-threatening bleeding event
- Febrile neutropenia

Dosing may be reinstated following dose interruption using the re-start schema detailed in below.

10.1 Dose Adjustments.

In order to provide sufficient data to make the dose adjustment decisions, it is recommended that hematology parameters be obtained weekly and at least two times weekly for platelet count $< 25,000/\mu L$ or ANC $< 500/\mu L$. In the event that any subject permanently discontinues the study drug, regardless of reason, reasonable efforts should be made to have the subject return for an early termination visit. If the drug discontinuation is being contemplated for a reason other than low platelet count or

low ANC, the use of a tapering strategy should be considered (see below). The date the subject discontinued the study drug and the specific reason for discontinuation will be recorded in the eCRF; eg, reasons such as discontinued due to inadequate efficacy or withdrawn due to adverse event. This information will be used to summarize the reasons for study discontinuation. Efforts will be made to follow subjects who discontinue from the study in order to determine overall survival and leukemia free survival. Investigators will contact subjects every 6 months to determine if subjects have undergone leukemic transformation, or death, and for the latter, the cause of death.

10.2 Dose Adjustments in Ruxolitinib Tablets for Safety.

Dose adjustments apply to the phase 2 portion of this study. There are no dose adjustments allowed during phase 1. Dosing must be held if platelet counts decline below 10,000/μL or if a life-threatening bleed occurs with a platelet count below 20,000/μL. Doses must be decreased for platelet count values that decline greater than 50% of baseline and are greater than 25,000/μL to 75% of the defined MTD. Doses must be decreased for platelet count values that decline greater than 50% of baseline and are below 25,000/μL to 50% of the defined MTD. The dosing scheduled should be maintained at BID dosing to assure appropriate pharmacokinetics. Dose reductions should be executed by decreasing the individual dose and not the frequency of administration. In order to provide sufficient data to make the dose adjustment decisions, it is recommended that hematology parameters be obtained as defined in section 10.1. Dosing may be restarted or increased following recovery of platelet counts to acceptable levels. The following is the recommended dose restart/increase strategy:

In subjects whom drug was held, ruxolitinib may be restarted at 50% of the MTD after platelet count has improved to pre-ruxolitinib baseline levels and/or febrile neutropenia has resolved for at least 2 weeks. In subjects whom drug dose was decreased, ruxolitinib may be increased to the previous dose (MTD) after platelet count has improved to pre-ruxolitinib baseline levels and/or febrile neutropenia has resolved for at least 2 weeks. If criteria is met for discontinuation/dose modification then ruxolitinib must be discontinued with no potential for restart. The objective for

restarting or escalating after a reduction for safety is to find the highest safe dose of ruxolitinib for each subject, with increases in dose generally not more than in increments of 5 mg BID and not more often than every 2 weeks. Subjects who were not enrolled in the MTD cohort can increase to the MTD after week 17 if the participant still meets the eligibility criteria. Non hematological toxicity dose adjustment criteria

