and flow cytometry analysis. 4. Laboratory assessments: • Hematology to include platelet count, hemoglobin, hematocrit, white blood cells (WBC) and WBC differential (including: neutrophils, eosinophils, basophils, lymphocytes and monocytes), INR, PT, PTT, and reticulocyte count. • Clinical chemistries including BUN/urea, creatinine, sodium, potassium, alkaline phosphatase, alanine aminotransferase (ALT), aspartate aminotransferase (AST), total bilirubin, total bilirubin, albumin. • Urine or serum pregnancy test for females of childbearing potential will be performed at Screening or on Day 1, prior to first dose of study medication. 5. Review and record any blood and blood supportive care products for the prior 8 weeks. Treatment will be administered on an outpatient basis. Reported adverse events and potential Treatment risks are described in Section 11. Appropriate dose modifications for ruxolitinib are described in nlan Section 10. No investigational or commercial agents or therapies other than those described below may be administered with the intent to treat the patient's CMML. Ruxolitinib will be supplied by INCYTE as 5mg tablets containing ruxolitinib. Ruxolitinib will be self-administered as a twice-daily oral dose for a continuous treatment cycle. Ruxolitinib tablets will be taken approximately 12 hours apart (morning and night). Subjects will not take the morning dose of ruxolitinib at the first regularly scheduled visit. Drug will be administered in the clinic in order to obtain adequate biomarker assessment. On all other days corresponding to study visits, subjects will take the morning dose of study drug prior to the visit, and will note on the subject reminder card the time that medications were taken. Subjects will also be instructed to take ruxolitinib without respect to food, as previous data demonstrate no change in drug kinetics or absorption. The first patient will be given 10 mg/day divided in equal BID doses. Dose escalation guidelines are detailed below in section 10. In phase II of the study, a maximum of 29 subjects will be treated at the MTD identified in phase I. See study calendar for assessment on study. All subjects enrolled in phase 1 will start treatment on the assigned dose per cohort based on the Dose delay/modif dose escalation algorithm provided. Dose delays/modifications will not be allowed in phase 1 as it -ications will interfere with the primary endpoint of this study. Dose delays/modifications are allowed for those subjects enrolled in phase II as described in section 6. Definition Dose-limiting toxicity (DLT) is defined as any grade 4 hematologic toxicity and any grade 3 or of Dosegreater non-hematologic toxicity except nausea that is controlled by antiemetic therapy based on Limiting the NCI Common Terminology Criteria for Adverse Events (CTCAE) version 4.0. Grade 3 metabolic/electrolyte abnormalities that are not clinically significant, and are adequately Toxicity controlled within 72 hours are not to be considered a DLT. To discern disease specific versus drug specific myelosuppression, Grade 4 thrombocytopenia will be defined as a decrease of > 50% of baseline and a level of < 25,000/uL. Grade 4 neutropenia will be defined as a decrease of $\ge 50\%$ of baseline and a level of <500/uL. Subjects will be evaluated for DLTs during the first and second cycles of therapy, i.e. 8 weeks for purpose of deciding the dose for next cohort (see dose escalation schema) but DLTs will continue to be evaluated and reported through all cycles on **Duration of** Subjects will be treated for a total of 16 weeks. For subjects responding at week 16, treatment may continue until one of the following criteria applies: **Therapy** Dose-limiting toxicity is reached, Inter-current illness that prevents further administration of treatment, Unacceptable adverse event(s), Patient decides to withdraw from the study, or General or specific changes in the patient's condition render the patient unacceptable for further treatment in the judgment of the investigator. Evidence of disease progression by the IWG 2006 criteria. Subjects who wish not to continue treatment will complete their end of study visit at week 16.

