6.5.1.4 Medications that are inhibitors of CYP3A4

When concomitant administration of a potent systemic inhibitor of CYP3A4 metabolizing enzymes (ketoconazole, clarithromycin, itraconazole, nefazodone and telithromycin, see section 7) that is required for subject management, the dose of ruxolitinib tablets must be adjusted as described in section 7. Based on the low overall bioavailability of topical ketoconazole, with very low systemic levels seen following topical administration, no dose adjustment of ruxolitinib is needed for use with topical ketoconazole.

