10.3 Dose Reductions for Concomitant CYP Inhibitor Usage

Ruxolitinib is metabolized in the liver by the cytochrome (CYP) P450 metabolizing enzyme system, predominantly by the 3A4 isozyme. With concomitant dosing of potent CYP3A4 inhibitors such as systemic ketoconazole (see Appendix C), plasma exposure of Ruxolitinib increases approximately 2-fold. Thus, a dose reduction of ~ 50% for Ruxolitinib is appropriate for subjects who take systemic ketoconazole or other potent CYP3A4 inhibitors systemically as concomitant medication. BID doses will be decreased to the corresponding once daily dose as follows:

- If dose is 20 mg BID, change dose to 20 mg QD
- If dose is 15 mg BID, change dose to 15 mg QD
- If dose is 10 mg BID, change dose to 10 mg QD
- If dose is 5 mg BID, change dose to 5 mg QD
- If dose is 5 mg QD, no dose change is required.

Potent inhibitors of CYP3A4 include systemic ketoconazole, clarithromycin, itraconazole, nefazodone and telithromycin. NOTE: once the course of therapy using a CYP3A4 inhibitor has been completed, the subject should resume his/her prior BID dose regimen of study drug beginning the next day.

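### The phase 1 ban on dose changes conflicts with a mandatory CYP3A4 dose adjustment that names no phase, and no rule says how an affected subject counts in the DLT table

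*Combined protocol and SAP*

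**What the plan says.** The phase 1 ban appears three times. Section 10 says "No dose delays or modifications are allowed during this period". Section 10.2 says "There are no dose adjustments allowed during phase 1". The synopsis gives the reason: dose changes "will interfere with the primary endpoint of this study", which for phase 1 is the MTD.

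Section 6.5.1.4, under permitted medications, says that when a potent systemic CYP3A4 inhibitor is required, "the dose of ruxolitinib tablets must be adjusted as described in section 7". The Appendix C footnote also makes reductions mandatory for strong inhibitors. Neither names a phase. The prohibited list in 6.6 covers CYP3A4 inducers but not inhibitors.

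Section 10.3 says "BID doses will be decreased to the corresponding once daily dose as follows" and lists 20, 15, 10 and 5 mg BID (and 5 mg QD, unchanged). It gives the reason that with a potent inhibitor "plasma exposure of Ruxolitinib increases approximately 2-fold". Its own text names no phase, but it sits under a Section 10 lead-in that reads "All subjects enrolled in the phase 2 portion may have the following dose delays/modifications once the MTD has been defined".

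Escalation (6.3 and 6.3.1) uses DLTs over 8 weeks: 1 of 6 allows escalation, and 2 or more of 6 ends it, with the MTD set one level lower. Section 15.1 replaces subjects who drop out early for reasons other than a DLT.

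**The concern.** Site staff treating a phase 1 subject who needs a potent CYP3A4 inhibitor cannot follow both the ban and the adjustment rule. The two choices give different exposures, and the plan does not say how the subject counts under either. If the ban is followed, the subject's 8-week result is entered at the nominal level although exposure is nearer that of a higher dose. The MTD from phase 1 is the dose given to up to 29 subjects in phase 2, so a wrong escalation decision carries forward.

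**Working it through.** The plan states no figure on this point, so the check compares the rules and then illustrates the effect on the escalation rule.

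**Step 1: the rules side by side.**

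| Place | Rule | Phase named? | Inside Section 10? |
|---|---|---|---|
| Synopsis | no delay or modification | phase 1 | no |
| Section 10 | no delay or modification | phase 1 | yes |
| 10.2 | no adjustment | phase 1 | yes |
| 6.5.1.4 | adjustment mandatory with potent inhibitor | none | no |
| Appendix C footnote | reduction mandatory with strong inhibitor | none | no |
| 10.3 | BID changed to QD with potent inhibitor | none | yes, after the phase 2 lead-in |

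The lead-in may confine 10.3 to phase 2. It cannot confine 6.5.1.4 or Appendix C, which lie outside the section. The conflict therefore does not depend on how Section 10 is read.

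**Step 2: cross-references.** Both 6.5.1.4 and Appendix C send the reader to section 7, which is duration of therapy and holds no CYP3A4 dose rule. Section 6.2 sends the reader to Section 11 for dose modifications, but Section 11 is adverse event reporting. Neither settles the question.

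**Step 3: exposure.** Inputs are the phase 1 levels of 10, 20, 30 and 40 mg/day (6.2.1) and the 2-fold figure (10.3). Exposure is taken as proportional to dose, as the roughly 50% reduction in 10.3 implies.
- Ban followed: 2 × 10, 20, 30, 40 gives exposure like about 20, 40, 60, 80 mg/day. The last two lie above the top planned level.
- 10.3 followed: 2 × 0.5 = 1.0, so exposure stays near nominal.

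**Step 4: the escalation rule.** Let p be the DLT rate at the nominal level and q the rate in one affected subject. With six unaffected subjects,

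P(0 or 1 DLT) = (1−p)^6 + 6p(1−p)^5.

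With one affected subject, put A = (1−p)^5 and B = 5p(1−p)^4. Then

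P(0 or 1 DLT) = A + B(1−q).

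For p = 0.15 and q = 0.33: A = 0.4437 and B = 0.3915, so P = 0.4437 + 0.3915 × 0.67 = 0.706, against 0.776 with none affected. All rates are assumptions; the documents give none.

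| p | q (unadjusted inhibitor user) | none affected | one affected |
|---|---|---|---|
| 0.10 | 0.33 | 0.886 | 0.810 |
| 0.15 | 0.33 | 0.776 | 0.706 |
| 0.15 | 0.50 | 0.776 | 0.639 |
| 0.20 | 0.50 | 0.655 | 0.532 |

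The opposite direction applies if a subject's drug is held in the window and the DLT risk falls. With p = 0.33, P(0 or 1 DLT) is 0.358 with none held. With one held it is 0.413 if that subject's risk halves and 0.468 if it falls to zero.

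**Step 5: counting rules.** Sections 9.3 and 15.1 cover a subject with a DLT (treatment stops) and a subject who drops out without one (replaced). No section covers a subject who stays on study without a DLT but was held, adjusted, or left unadjusted on an inhibitor.

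**The case against.** The strongest reply is that every modification rule belongs to phase 2. The lead-in to Section 10 supports this for 10.3 and 10.4. The synopsis also says that phase 2 modifications are described in section 6, which could pull 6.5.1.4 into phase 2. The first part has force. The second does not hold up well: the synopsis and 6.1 both point to Section 10 for dose modifications, and that is where the detailed rules are, so the section 6 reference is at best a possible slip. It leaves the Appendix C footnote untouched.

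A second reply is that the investigator may discontinue a subject at any time (9.2), and 15.1 would then replace a dropout. That permits a way out but does not direct it, and it says nothing about a subject who stays on treatment.

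A reader might also infer that the investigator's discretionary hold, the mandatory halts and the hepatic hold contradict the phase 1 ban. The documents do not support that firmly. The discretionary hold and the halts come directly after the phase 2 lead-in. The hepatic rule in 10.4 restarts at half of an MTD that does not exist during escalation. The platelet halt (below 10,000/µL) from an entry floor of 35,000/µL is a fall of more than 1 − 10/35 = 71%, so it already meets the DLT definition and cannot hide an event. These items need a stated phase; they are not evidence of a contradiction.

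**Conclusion.** The conflict between the phase 1 ban and the CYP3A4 adjustment rule stands on any reading of Section 10, and the plan lacks a counting rule for the subjects it affects. It should be corrected, but it does not undermine the design.

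On the protocol's own 2-fold figure, an unadjusted inhibitor user is one or more dose steps above the nominal level. In the assumed scenarios, one such subject in six lowers the chance of 0 or 1 DLT by 0.07 to 0.14.

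Two stronger readings are tempting and should be resisted. One is that the DLT counts are distorted. The documents support only that they can be: they give neither the frequency of inhibitor use nor DLT rates, and the shift can go either way. The other is that a subject whose dose is halved under 10.3 is counted at the wrong exposure. The halving offsets the 2-fold increase, so that subject stays near nominal; for CYP3A4, the problem lies with the unadjusted subject.

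**What to change.** 1. Reconcile the synopsis, Section 10 and 10.2 with 6.5.1.4, 10.3 and Appendix C by stating which rules apply in phase 1. State whether the hepatic hold in 10.4 and the investigator hold are phase 2 only. Correct the references to section 7 (6.5.1.4, Appendix C) and to Section 11 (6.2). Which clinical rule prevails is for the sponsor to decide.

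2. In 15.1, prespecify how affected phase 1 subjects count at the nominal level over the 8-week window:
- Any observed DLT is retained.
- A subject without a DLT whose drug was held in the window, or who took a potent inhibitor without a matching adjustment, is not evaluable and is replaced.
- A subject whose dose change offsets the inhibitor stays evaluable.

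A rule that replaced everyone with a dose change would discard subjects near nominal exposure and keep the one at double exposure, so the distinction matters.

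The cost is protocol wording and an occasional replacement subject.

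### Sections 10 and 10.2 state different mandatory hold criteria for a life-threatening bleed in phase 2 when platelets are 20,000/µL or more

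*Combined protocol and SAP*

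**What the plan says.** Section 10 opens by ruling out delays and modifications in phase 1 and allowing those that follow in phase 2. It then gives a permission: "Ruxolitinib may be held by the Investigator at any time if there is concern about subject safety". Next comes a mandatory rule: "Dosing must be halted immediately if either of the following occurs". The first listed trigger is a platelet count below 10,000/µL "and/or a life-threatening bleeding event"; the second is febrile neutropenia. The bleed carries no platelet condition.

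Section 10.2 limits itself in its first sentence: "Dose adjustments apply to the phase 2 portion of this study". Its hold rule has two limbs: "Dosing must be held if platelet counts decline below 10,000"/µL, or "if a life-threatening bleed occurs with a platelet count below 20,000"/µL. Two mandatory decreases follow, both triggered by platelet decline:

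- "Doses must be decreased for platelet count values that decline greater than 50% of baseline and are greater than 25,000"/µL: to 75% of the MTD.
- "Doses must be decreased for platelet count values that decline greater than 50% of baseline and are below 25,000"/µL: to 50% of the MTD.

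Neither section says which governs, and neither explains the 20,000/µL condition.

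**The concern.** The platelet-only trigger is the same in both places, but the bleed trigger is not. Someone working from Section 10 halts for every life-threatening bleed. Someone working from 10.2, whose title marks it as the place for safety-related dose adjustment, finds a hold for that bleed only under 20,000/µL and may find a mandatory dose decrease above it.

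This is a safety rule that must be applied at once, so it should read the same wherever it is looked up. There is also a smaller consequence for the data. Section 17.6 refers to subjects at other institutions as well as the sponsor's, so readings can differ by site. Section 10.1 summarises reasons for discontinuation and Section 15.4 reports adverse events leading to discontinuation. Whether an event was handled as a hold, a reduction or a discontinuation therefore affects exposure and could reach the reported safety tables.

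**Working it through.** The plan gives no figure to reproduce. The check sets the two rules side by side for one event, a life-threatening bleed in a phase 2 subject, across platelet counts.

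**Inputs.** Halt rule: Section 10. Hold and decrease rules: Section 10.2. Entry floor: counts below 35,000/µL are excluded (Section 4.2.1.1). Phase 2 size: at most 29 (Section 6.1.2). DLT definition: Section 6.2. Discontinuation for a DLT: Section 9.3.

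| Platelets at the bleed | Section 10 | Section 10.2 |
|---|---|---|
| Below 10,000/µL | Halt | Hold |
| 10,000 to below 20,000/µL | Halt | Hold |
| 20,000 to below 25,000/µL, fall of more than 50% | Halt | No hold stated; decrease to 50% of MTD |
| Above 25,000/µL, fall of more than 50% | Halt | No hold stated; decrease to 75% of MTD |
| 20,000/µL or more, no such fall | Halt | No mandatory action stated |

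A count of exactly 25,000/µL meets neither decrease rule as worded, so it belongs with the last row.

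**Which baselines reach the decrease rows.** A fall of more than 50% means count < 0.5 × baseline, that is, baseline > 2 × count.

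- At 20,000/µL or more, a decrease rule can apply only if baseline > 2 × 20,000 = 40,000/µL.
- Above 25,000/µL, it can apply only if baseline > 2 × 25,000 = 50,000/µL.
- For a subject entering at 35,000/µL, half of baseline is 17,500/µL, already under 20,000/µL. Any bleed at 20,000/µL or more in that subject falls in the last row.

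**Example.** Take a baseline of 60,000/µL, so half is 30,000/µL. A bleed at 22,000/µL is a fall of (60,000 − 22,000)/60,000 = 63%. Section 10 requires an immediate halt; 10.2 calls for 50% of the MTD. For the same subject, 10.2 gives 75% of the MTD for counts above 25,000 and below 30,000/µL, and no mandatory action from 30,000/µL up. Section 10 requires a halt throughout.

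**Why the label matters afterwards.** Under 10.2 a held subject may restart at 50% of the MTD, while a reduced subject may go back up to the MTD. The recovery conditions are platelet count and resolved febrile neutropenia; none is given for a resolved bleed. Section 10.2 also describes later stepwise increases, so the restart level is not necessarily permanent, but the two routes differ.

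**A possible further instruction.** If the bleed is graded 3 or higher as a non-hematologic toxicity, it meets the DLT definition in Section 6.2, whose exceptions do not include bleeding. Section 9.3 lists a DLT among the reasons treatment must be discontinued, whereas Section 10 allows dosing to be reinstated after an interruption.

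**The case against.** The strongest reply is that 10.2 states when a hold is required and does not say that it is required in no other case. A site that halts under Section 10 breaches no hold rule in 10.2. The decrease rules respond to platelet decline, not to bleeding, and they already overlap the hold rule inside 10.2: a count of 8,000/µL after a fall of more than half meets both, and the natural reading is that the hold prevails. Other text also covers the event: the investigator may hold at any time, and Section 9.3 requires discontinuation for a DLT or when the investigator judges continuation an unacceptable risk.

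Part of this stands. A reader might infer that the two sections give opposite orders. The documents do not support that: 10.2 nowhere tells a site to keep dosing through a life-threatening bleed, and where the fall is 50% or less it is simply silent. It is also unlikely that a subject would stay on drug solely because of the 20,000/µL condition.

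The rest does not remove the problem. If Section 10 always governs, the 20,000/µL condition has no function, yet a reader of 10.2 would reasonably take it as a real limit. That a hold overrides a decrease is sensible but unwritten. A permission to hold does not make two mandatory rules agree, and the DLT route depends on how the bleed is graded and may lead to a different outcome from either section.

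**Conclusion.** The inconsistency is real and confined to phase 2. For a life-threatening bleed at 20,000/µL or more, Section 10 requires a halt and 10.2 states none. Where platelets have also fallen by more than half from baseline, 10.2 calls for a decrease to 50% or 75% of the MTD, and that classification changes the route back to dose. Below 20,000/µL the sections agree.

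The size is small in numbers: at most 29 subjects are treated in phase 2, and only those who have such a bleed at such a count are affected. The documents give no rate of life-threatening bleeding in CMML, so no expected count can be stated. The case for correction rests on the seriousness of the event, not its frequency.

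Two wider inferences should not be drawn. Because entry requires at least 35,000/µL, a reader might say every subject starts in the disputed range; but the wording matters only when a life-threatening bleed occurs, not at baseline. Nor do the criteria select a thrombocytopenic population: they set a minimum count, not a maximum.

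The conclusion assumes that the 20,000/µL condition was meant to do something. The point about Section 9.3 assumes the bleed is graded 3 or higher as a non-hematologic toxicity. No endpoint, sample size or planned analysis changes.

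**What to change.** Reconcile Sections 10 and 10.2 so that one hold criterion for life-threatening bleeding appears in identical words in both, and check it against the DLT discontinuation rule in Section 9.3 so that the same event does not lead to a different instruction there. In the same edit, state that a required hold takes precedence over a required decrease if that is what is meant, and say how the restart text applies after a bleed. The clinical team must decide which criterion applies; this review takes no position. The core change costs about one sentence in the protocol, with no effect on sample size or analysis.
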